9.5.12. Mortality and Protocol-Defined AESI

Mortality status will be derived from the SAE data, where outcome is fatal.

The derivation for the protocol-defined AESIs are provided in the table below. Treatment emergent AESIs (see Section 9.5.13 and Section 9.5.15) only will be summarized.

Where the protocol defined AESI utilize definitions from the PSAP, the detailed derivations from the PSAP are provided in [Appendix 6: PSAP Sections for AESI Reporting](#). AESI are identified per the preferred terms and other criteria described in the PSAP.

Protocol-Defined AESI (see Section 2.2.1 and Section 2.2.3 for clarification)	Definition	Programming Derivation (Protocol Definition)
Serious infections	SAEs within Infections and Infestations SOC.	SOC=Infections and Infestations & AESER = 'Y'
Opportunistic infections and other infections of interest	"All Infections" per PSAP definition to cover all OI and infections of interest.	CQ06NAM ne " or CQ07NAM ne " or CQ08NAM ne "
Non-melanoma skin cancers (NMSC)	NMSC per PSAP definition.	CQ00MLFL = 'Y' and CQ03NAM ne " and CQ03NMFL = 'Y'
Malignancies (excluding NMSC)	PSAP defined, "all malignancies excluding NMSC".	[CQ00MLFL = 'Y' and (CQ01NAM ne " or CQ02NAM ne " or (CQ03NAM ne " and CQ03NMFL ne 'Y'))] Or (CQ04NAM ne " and CQ04NPFL = 'Y')
Psychiatric events suggesting serious mood disorders and anxiety	Serious events from the depression CMQ (PSAP defined – depression including mood disorders and anxiety).	CQ09NAM ne " and AESER = "Y"
Suicidality (C-SSRS)	Any treatment-emergent C-SSRS suicidal ideation (1-5) or suicidal behavior (6-10) (defined in Section 9.5.15) – i.e. maximum ideation score worsens relative to pre-treatment or maximum behavior score worsens relative to pre-treatment	C-SSRS Ideation categories 1-5 and Behavior categories 6-10; any subject with ideation or behavior that is treatment-emergent (defined in Section 9.5.15).
Serious infusion and hypersensitivity reactions	Serious infusion and hypersensitivity reactions per the PSAP definition. Includes all SAEs from the anaphylactic reactions CMQ broad search (see Section 11.2.4, includes events on the day of the infusion or within 3 days after the infusion).	CQ05NAM ne " and AESER='Y' and AEINF3FL='Y'

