9.5.13. Treatment-Emergent AEs and AE Duration

Only treatment-emergent AESIs and SAEs, will be summarized, unless otherwise stated. A treatment-emergent AE is an AE that emerges on or after the first treatment dose, having been absent pre-treatment, or that worsens relative to the pre-treatment state.

The duration of the AE will be calculated as follows:

Duration of AE (days) = Date of AE resolution – AE start date + 1.

If the AE is ongoing the duration will be left blank and no imputation will be done.

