9.5.15. Treatment-Emergent C-SSRS

For suicidal ideation, the pre-treatment reference period is the lifetime history, current history and baseline (for further detail refer to the IDSL documentation). For suicidal behavior, the pre-treatment reference period is the lifetime history and baseline (note: suicidal behavior is not re-assessed for the current history time period).

Suicidal ideation and suicidal behavior will be considered as distinct categories and assessed independently of each other. Treatment emergence will be assessed for the on-treatment period and the on-study period.

Suicidal ideation will be assessed using responses to C-SSRS ideation questions (categories 1 to 5) only. Suicidal behavior will be assessed using responses to C-SSRS behavior questions (categories 6 to 10) only.

- **Treatment emergent suicidal ideation** will be assessed using the maximum ideation score pre-treatment, compared to the maximum ideation score post-treatment (on-treatment or on-study as appropriate). If the maximum ideation score worsens relative to the pre-treatment reference period then this will be considered a treatment emergent suicidal ideation. This is derived from responses to suicidal ideation questions (categories 1 to 5).
- **Treatment emergent suicidal behavior** will be assessed using the maximum behavior score pre-treatment, compared to the maximum behavior score post-treatment (on-treatment or on-study as appropriate). If the maximum behavior score worsens relative to the pre-treatment reference period then this will be considered a treatment emergent suicidal behavior. This is derived from responses to suicidal behavior questions (categories 6 to 10).
- **Treatment emergent suicidal ideation or behavior** will be defined as a subject having a treatment emergent suicidal ideation (as defined above) and/or a treatment emergent suicidal behavior (as defined above). This definition is used to assess the protocol defined AESI endpoint of ‘Suicidality (C-SSRS)’ (see Section 9.5.15).

Suicidal Ideation (categories):

1. Wish to be Dead
2. Non-Specific Active Suicidal Thoughts
3. Active Suicidal Ideation with Any Methods (Not Plan) without Intent to Act
4. Active Suicidal Ideation with Some Intent to Act, Without Specific Plan
5. Active Suicidal Ideation with Specific Plan and Intent

Suicidal Behavior (categories):

6. Preparatory Acts or Behavior
7. Aborted Attempt
8. Interrupted Attempt
9. Non-Fatal Actual Suicide Attempt
10. Completed Suicide

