11.1.1. All-Cause Mortality

See Section 11.2.1 and Section 11.2.2 for further summaries and listings of deaths.

Percentages

A summary of the number and percentage of subjects who have died will be provided for belimumab and placebo as well as the difference in the percentage of subjects between the belimumab and placebo groups. The difference in percentages will be evaluated with a 2-sided 95% CI, using the simple asymptotic Chi-Square (Pearson) method [Newcombe, 1998]. This will be considered as the primary method of assessment of the treatment difference.

Subject Incidence Rate

Whilst a difference between belimumab and placebo groups in IP exposure and overall study duration (to Week 52) is not anticipated, to account for this, supplemental summaries using subject incidence rates will be provided.

The subject incidence rate of mortality per 100 subject years will be provided for belimumab and placebo as well as the difference between belimumab and placebo with 95% CIs. For within-group rates per 100 subject years, the 95% CI will be obtained via

on an exact Poisson method [Stokes, 2012]. For differences in rates between groups, the 95% CI will be constructed using a Normal approximation (Wald's method, [Liu, 2006]).

See Section 9.5.14 for further details on the calculation of incidence rates for the on-treatment and on-study periods.

Kaplan-Meier Figure

A plot of the Kaplan-Meier curve, including standard error bands, for all-cause mortality for belimumab and placebo will be provided to show the change in risk over time. The Kaplan-Meier estimates table will be outputted for quality control purposes but will not be used included in the tables or listings.

Time to Event is defined for the On-Treatment Period and On-Study Period as follows:

- For subjects who died during the evaluation period of interest (i.e. on-treatment or on-study): Time to event is the date of death - first exposure date + 1.
- For subjects who did not die or died after the end of the evaluation period of interest (i.e. on-treatment or on-study): Time to event (censored) is the censoring date – first exposure date + 1.

Occurrence and date of death will be determined based on the AE dataset where outcome = fatal (date of death will be derived as the end date of the SAE with fatal outcome).

The censoring date will be assigned based on the evaluation period of interest as follows:

- **On-treatment:** end date for On-Treatment period (see Section 9.1.1)

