11.1.2. Protocol-Defined AESI

Protocol-defined AESIs are defined in Section [9.5.12](#).

Note, for Suicidality (C-SSRS) only, a subject must have at least one pre-treatment C-SSRS assessment (screening and/or baseline) and at least one on-treatment C-SSRS assessment (post-baseline) to be included in the summaries.

Percentages

For each of the AESIs a summary of the number and percentage of subjects experiencing at least one event will be provided for belimumab and placebo as well as the difference in the percentage of subjects (and 95% CI) between the belimumab and placebo groups using the same methodology as for mortality.

Subject Incidence Rate

The incidence rate for each AESI per 100 subject years will be provided for belimumab and placebo groups as well as the difference between placebo and belimumab (and 95% CI) using the same methodology as for mortality.

Event Incidence Rate

The number of events and event rate for each AESI, except Suicidality (C-SSRS), per 100 subject years will be provided for belimumab and placebo groups.

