11.2.4. PSAP-Defined Adverse Events of Special Interest

The PSAP has been developed to include AESI summaries for consistent reporting across belimumab studies which will be included here in addition to the primary summary of overall AESI rates described in Section 11.1.2 of this RAP.

Categorizations for the AESIs from the PSAP are defined [Appendix 6: PSAP Sections for AESI Reporting](#) and reporting of AESIs for these analyses is defined below.

An overall summary of AESI will be presented. Selected categories of AESI will be presented separately by PT. Infection AESIs will also be presented by PT for infections leading to discontinuation of study agent. The number and percentage of subjects with at least one occurrence and the number of events of the following AESI will be provided.

- Malignant Neoplasms
 - Malignancies Excluding non-melanoma skin cancer (NMSC) [see Section 9.5.12, protocol defined AESI]
 - Malignancies Including NMSC
 - Solid Tumour
 - Hematologic
 - Skin (All)
 - NMSC [see Section 9.5.12, protocol defined AESI]
 - Excluding NMSC
 - Tumours of unspecified malignancy adjudicated as malignant per GSK adjudication
- Post-Infusion Systemic Reactions
 - Post-Infusion Systemic Reactions per Anaphylactic Reaction Customized MedDRA Query (CMQ) narrow search (on the day of the infusion or within 3 days after the infusion)
 - Serious Post-Infusion Systemic Reactions per Anaphylactic Reaction Customized MedDRA Query (CMQ) narrow search (on the day of the infusion or within 3 days after the infusion)

- Post-Infusion Systemic Reactions per Anaphylactic Reaction CMQ broad search (on the day of the infusion or within 3 days after the infusion)
 - Serious Post-Infusion Systemic Reactions per Anaphylactic Reaction CMQ broad search (on the day of the infusion or within 3 days after the infusion) [see Section 9.5.12, protocol defined AESI]
 - Post-Infusion Systemic Reactions per Anaphylactic Reaction CMQ algorithmic search (on the day of the infusion or within 3 days after the infusion)
 - Serious Post-Infusion Systemic Reactions per Anaphylactic Reaction CMQ algorithmic search (on the day of the infusion or within 3 days after the infusion)
 - Serious Anaphylaxis per Sampson Criteria
 - Serious Acute Post-Infusion Systemic Reactions/Hypersensitivity per GSK adjudication
 - Serious Acute Post-Infusion Systemic Reactions Excluding Hypersensitivity per GSK adjudication
 - Serious Acute Hypersensitivity Reactions per GSK adjudication

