11.2.5.1. C-SSRS Suicidal Ideation or Behavior

The number and percentage of subjects with suicidal ideation or behavior at any time during the on-treatment and on-study (to Week 52) periods will be presented. For suicidal ideation, the maximum ideation score (1-5) at any time during the relevant period will be presented. For suicidal behavior, all behaviors (6-10) present at any time during the relevant period will be presented. This will be regardless of whether the subject had pre-treatment history (up to and including baseline [see Section 9.5.1 for baseline definition]). The categories of suicidal ideation and behavior are presented in increasing order of severity from 1 to 5, and 6-10 respectively.

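### Does measuring on-study suicidality against each subject's lifetime history leave the trial without a sound between-arm suicidality comparison?

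*SAP*

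**What the plan says.** Section 11.1.2 of the Week 52 RAP gives, for each protocol-defined AESI, the number and percentage of subjects with an event "as well as the difference in the percentage of subjects (and 95% CI) between the belimumab and placebo groups". The method is the one set for mortality in Section 11.1.1: "The difference in percentages will be evaluated with a 2-sided 95% CI, using the simple asymptotic Chi-Square (Pearson) method".

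Section 9.5.12 defines the suicidality AESI as any treatment-emergent C-SSRS ideation or behavior, that is, "maximum ideation score worsens relative to pre-treatment or maximum behavior score worsens relative to pre-treatment". Section 9.5.15 states the rule for behavior: "If the maximum behavior score worsens relative to the pre-treatment reference period then this will be considered a treatment emergent suicidal behavior". It also fixes the reference: "For suicidal behavior, the pre-treatment reference period is the lifetime history and baseline". For ideation, the current-history period is added.

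Three other displays cover suicidality, all without a difference or CI:

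- Section 11.2.5.1 tabulates on-treatment and on-study ideation and behavior, and says of this: "This will be regardless of whether the subject had pre-treatment history".
- Section 11.2.5.3 cross-tabulates the worst pre-treatment category against the worst on-treatment or on-study category.
- Section 11.2.4 covers the program-defined and sponsor-adjudicated suicide and self-injury categories: "The number and percentage of subjects with at least one occurrence and the number of events of the following AESI will be provided". This is Table 3.037, one of the headline results in Section 16.3.

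**The concern.** Protocol Section 1.3 names selected psychiatric events and suicidality among the areas where earlier controlled trials showed a numerical imbalance. Protocol Section 8.1 says the main purpose is to estimate AESI differences with 95% CIs. The only suicidality estimate that gets a CI is blind to some on-study behavior: a subject whose lifetime maximum is 9 (non-fatal actual attempt) and who makes another attempt on study scores 9 against 9 and does not count, unless ideation exceeds its own earlier maximum.

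Such subjects can enroll. Protocol Table 1-3 says this risk does not directly affect eligibility, and Section 7.4 expects that ideation or behavior may occur before the study. The other psychiatric AESI with a CI does not fill the gap, because its depression query starts from a standard query that excludes suicide and self-injury (Appendix 6, PSAP Section 15.4.1). At stake would be the sensitivity of the suicidality comparison to events in the subjects most likely to have them.

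**Working it through.** **1. What the rule removes.** Compare the on-study maximum with the pre-treatment maximum on the behavior scale (6 to 10):

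| Pre-treatment maximum | On-study maximum | Counted? |
|---|---|---|
| none | 6 to 10 | yes |
| 6, 7 or 8 | 9 (actual attempt) | yes |
| 9 | 9 (repeat attempt) | only if ideation also worsens |
| any of 6 to 9 | 10 (completed suicide) | yes |

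The loss is confined to behavior at or below the earlier maximum without worsened ideation. Completed suicide is never lost.

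**2. Whether the rule is out of line.** Section 9.5.13 defines a treatment-emergent AE as one that emerges on or after the first dose, "having been absent pre-treatment, or that worsens relative to the pre-treatment state". Section 9.5.15 applies the same idea to a scale score. The protocol endpoint is suicidality by C-SSRS, with no counting rule, so nothing is contradicted.

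**3. Whether it biases the comparison.** The reference uses only pre-treatment assessments; the Day 0 C-SSRS is done before infusion (protocol Table 6-1, footnote 3). The condition is identical in both randomized arms. It can lower sensitivity, but nothing in the documents suggests that the loss would differ by arm.

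**4. Whether the uncounted events are hidden.** In the Section 11.2.5.3 shift table each subject appears once, and a subject with both ideation and behavior is placed under behavior. The on-study margins therefore give:

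- any behavior = the behavior margin;
- any ideation or behavior = the ideation margin plus the behavior margin.

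Both are regardless of history and by arm. The body of the table also separates subjects with prior behavior from those without, which a pooled difference would not show. In addition, protocol Section 7.4.1.1 treats any behavior answered yes as an SAE, so these events also reach the SAE tables and adjudication.

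**5. Size.** Half-width of the simple asymptotic CI with equal arms: 1.96 × √(2p(1−p)/n).

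The plan's own figure comes first (Section 5.1):

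- p = 0.564%, n = 2,000: 0.464 points, stated as ±0.46.
- p = 0.68%, n = 2,500: 0.456 points, stated as ±0.46.

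Both reproduce. For suicidality, assume n = 2,000 per arm and read the program rates in protocol Section 1.2 (behavior 180, ideation 108 per 100,000 subject-years) as one-year proportions:

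| Composite rate per 100,000 | Subjects per arm | Half-width (points) | One subject (1/2,000 = 0.05 points) as share of half-width | As share of one arm's count |
|---|---|---|---|---|
| 180 (full overlap) | 3.6 | 0.263 | 19% | 28% |
| 180 + 108 = 288 (no overlap) | 5.8 | 0.332 | 15% | 17% |

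The C-SSRS asks at every visit and starts from the mildest ideation item, so actual counts may be higher. At assumed rates of 0.5% and 5% (not in the documents) there are 10 and 100 subjects per arm and half-widths of 0.437 and 1.351 points. One subject is then 11% and 4% of the half-width.

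Hypothetical example: 4 vs 4 of 2,000 gives 0.00 (−0.28 to 0.28) points. With one repeat attempter counted, 5 vs 4 gives 0.05 (−0.24 to 0.34). The reading is the same.

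**The case for a change.** The strongest case on the other side is that the loss need not be one subject. Suppose 10% of subjects have a history, the on-study rate is 5% in them and 0.5% in the rest, and 30% of events in those with a history exceed the earlier maximum. All three inputs are assumptions. The rate regardless of history is 0.10 × 5% + 0.90 × 0.5% = 0.95%. The treatment-emergent rate is 0.10 × 5% × 0.30 + 0.90 × 0.5% = 0.60%. The endpoint then omits 0.35/0.95 = 37% of subjects with any on-study ideation or behavior. Other assumed inputs (history in 5% to 20% of subjects, 10% to 30% of their events exceeding the maximum) give 24% to 64%.

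It can also be said that Section 2.2.3, which lists changes and clarifications to the protocol analysis, does not mention this choice, and that Section 11.2.5.2 notes the ceiling for ideation only.

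What stands: the treatment-emergent endpoint may be less sensitive than a count regardless of history, and the documents supplied plan no difference or CI for the latter. What does not follow is that the plan misleads. The endpoint answers a stated question about new or worsened suicidality. The broader counts are reported beside it by arm, and anyone can compute the difference from them. The RAP Addendum of 13-DEC-2018, which adds safety analyses for the same period, and the mock shells were not available, so it is also unknown whether such an interval is already planned.

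**Conclusion.** The concern does not hold. The treatment-emergent definition is a conventional, prespecified choice that conflicts with nothing in the protocol and treats both arms alike. The planned counts and shift table show the events it leaves out, and no stated number or rule needs correcting.

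The size of any loss of sensitivity is unknown. Per uncounted subject it is 0.05 points, or 15% to 19% of the CI half-width at the program rates, assuming 2,000 subjects per arm and rates read as one-year proportions. The share falls if C-SSRS counts are higher.

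A difference and CI on the counts regardless of history would be a reasonable supportive extra. Week 52 data were unblinded on 2-JAN-2019 (Years 2 to 5 RAP, Section 1), so unless the Addendum or shells already contain it, it would now be post hoc. Its absence leaves the planned analysis sound.

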9.5.16. Prednisone

All prednisone analyses and summaries will consider SLE-related steroids only but data will also be derived for all indications steroids (SLE and non-SLE) for reference where indicated below.

The following will apply to all derivations in this section unless otherwise stated:

- For steroid use analyses, all steroid dosages are converted to a prednisone equivalent in milligrams; therefore, analyses refer to average daily prednisone dose instead of average daily steroid dose. See [Appendix 4: Prednisone Equivalent Conversion](#) for instructions on converting steroids to prednisone equivalents.
- This appendix will be updated throughout the course of the study to include all corticosteroids taken by subjects and will be finalized prior to the first database release and unblinding.
- For all derivations of the average daily prednisone equivalent dose including baseline, days on which a subject does not have prednisone use recorded will be considered as 0 mg for the day.
- Steroids taken intravenously (IV), intramuscularly (IM), subcutaneously (SC), intradermally, and orally are considered in prednisone dose derivations only.
- All steroids taken on any given day, including overlaps, will be accounted for in calculations of average daily prednisone dose. To achieve this programmatically, each entry is converted to the prednisone equivalent daily dose (see [Appendix 4: Prednisone Equivalent Conversion](#)) and the sum of the prednisone equivalent doses on Day X gives the total prednisone equivalent daily dose on Day X. For example, if two steroids are given on the same day they will be converted to a prednisone equivalent daily dose and then added together to achieve a total for that day.

Steroids used to treat SLE are those with medication type corticosteroid for SLE (SDTM.CM.CMCAT = 'CORTICOSTEROID FOR SYSTEMIC LUPUS ERYTHEMATOSUS').

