9.4.3. Missing Data

Adverse Events (AESIs, Serious Adverse Events) and Concomitant Medications

Missing Dates

Element	Reporting Detail
General	Partial dates will be displayed as captured in subject listings.
Concomitant Medications	
 • Where medication start date (CMSTDT) is completely missing but medication end date (CMENDT) is on or after Day 1, the medication start date (CMSTDT) will be imputed as study treatment start date (TRTSDT). • Where medication start date (CMSTDT) is completely missing and medication end date (CMENDT) is missing and the medication is ongoing (CMONGO = “Y”), the medication start date (CMSTDT) will be imputed as study treatment start date (TRTSDT) and the medication will be considered as ongoing. 
Medication End Date (CMENDT) Missing end dates for concomitant medications will not be imputed, and the medication will be considered ongoing. For corticosteroids, the medication end date will be imputed as study completion or withdrawal date during the ADPRED dataset creation in order for those medications to be included in prednisone summaries. However, if the start date of the medication is greater than the study completion or withdrawal date, the end date will not be imputed.

Adverse Events	The eCRF does not allow for the possibility of missing or partial AE dates (except for missing AE end dates which are allowed if the AE is ongoing).

See Section 9.5.13 for further details on whether AE is considered as treatment-emergent.

Other than described above, missing data will not be imputed unless stated otherwise for an individual endpoint.

A missing category will be added to frequency counts if there is at least one missing record.

Partial Dates

Element	Reporting Detail
Date of Birth	
 • Only year of birth is collected on the eCRF. • Day will be set to 30 and month will be set to JUNE for all subjects.

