Concomitant Medications	
Medication Start Date (CMSTDT) Medication start date (CMSTDT) is imputed as study treatment start date (TRTSDT) unless:
 
 • CMENDT is < TRTSDT, whether CMENDT is complete (DD/MM/YY) or partial (some combination of CMENDT day, month or year imputed) OR • The month or month and year of the partial CMSTDT are different from the month and/or year of TRTSDT OR • “Taken prior to study?” is checked. 
If any of the above conditions are met then medication start date (CMSTDT) is imputed with JAN for missing month and 01 for missing day, whatever is applicable.
 
Medication End Date (CMENDT)
 
 • If month and year are present, then: 
 • If the medication started on or after study withdrawal or completion then set to the last day of that month. • If the medication started prior to study withdrawal or completion set to the last day of that month, unless the end month and year are the same as the month and year of the study withdrawal or completion date, in which case set to the study withdrawal or completion. date. • If only year present, then: 
 • if the medication started on or after study withdrawal or completion then set to 31DEC. • if the medication started prior to study withdrawal or completion then set to 31DEC, unless the end year is the same as the year of the study withdrawal or completion date, in which case set to the study withdrawal or completion date.
Date of SLE diagnosis	
 • For records where month and day are missing for diagnosis date, impute with 01 for day and January for month to assume that the duration was the longest possible duration. • For records where the day only is missing for start date, impute with 01 for day to assume that the duration was the longest possible duration.

Element	Reporting Detail
Last known to be alive date	
 For records where month and day are missing for last known to be alive date, impute 01 for day and January for month. For records where the day only is missing, impute 01 for day.

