9.5.16.1. Average Daily Prednisone Equivalent

Prior to carrying out calculations, each steroid must be converted to its prednisone equivalent and then the daily dose calculated using the frequency factors provided in

[Appendix 4](#): Prednisone Equivalent Conversion. Days on which the subject has no steroid use will be considered as 0mg.

Baseline

At baseline, the average daily prednisone equivalent dose is the sum of all prednisone doses over 7 consecutive days up to, but not including Day 1, divided by 7.

This will be derived for both steroids used to treat SLE and steroids used to treat all indications (SLE and non-SLE) separately. The baseline average daily prednisone dose for all indications will not be reported but will be used to carry out a cross-check against the randomization strata, which were determined by sites based on steroids received for any indication.

Treatment completion average dose

The average daily prednisone dose is the sum of all prednisone doses over 7 consecutive days up to and including the date of treatment completion, divided by 7.

This will be derived for steroids received for SLE only.

9.5.16.2. Average Daily Prednisone Dose during Weeks 40 to 52

The average daily prednisone dose during Weeks 40 to 52 is the sum of all prednisone doses from the day following the Week 40 visit date up to but not including the Week 52 study completion date divided by the number of days between Week 40 visit date and study completion date (study completion date – Week 40 visit date).

For subjects who withdraw from the study prior to the Week 40 visit date, the average daily prednisone dose during Weeks 40 to 52 will be missing.

For subjects who withdraw from the study after the Week 40 visit date, the average daily dose will be calculated as the sum of all prednisone doses from the day after the Week 40 visit date up to and including the date of withdrawal or death, whichever is earlier divided by the number of days between Week 40 visit date and the date of withdrawal or death, whichever is earlier (date of withdrawal or death – Week 40 visit date + 1). If the Week 40 visit is missing for any subject who has not withdrawn or died prior to Week 40, the Week 40 visit date will be imputed as treatment start date + 40 * 7 for this derivation.

This will be derived for steroids received for SLE only.

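### Incomplete steroid stop dates can make the old and new dose count together after a dose change, which distorts the Week 40–52 steroid-reduction endpoint and sometimes the baseline

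*SAP*

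**What the plan says.** Three rules of the Week 52 RAP act together.

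- **Missing stop date (9.4.3).** "For corticosteroids, the medication end date will be imputed as study completion or withdrawal date during the ADPRED dataset creation", so that the record enters the prednisone summaries.
- **Partial dates (9.4.3).** For a stop date with month and year only: "If the medication started prior to study withdrawal or completion set to the last day of that month", or the completion/withdrawal date if that falls in the same month. A year-only stop date goes to 31 December, again capped at completion/withdrawal when the year is the same. A partial start date outside the month of treatment start "is imputed with JAN for missing month and 01 for missing day".
- **Summing (9.5.16).** "All steroids taken on any given day, including overlaps, will be accounted for in calculations of average daily prednisone dose", and "the sum of the prednisone equivalent doses on Day X gives the total prednisone equivalent daily dose on Day X".

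The major efficacy endpoint (12.1.1) takes subjects with a baseline average above 7.5 mg/day. It requires a Week 40–52 average that is at most 7.5 mg/day and at least 25% below baseline. Under 9.5.16.2 that average uses "prednisone doses from the day following the Week 40 visit date up to but not including the Week 52 study completion date". Its denominator is the difference in days between those two dates. Baseline (9.5.16.1) is "the sum of all prednisone doses over 7 consecutive days up to, but not including Day 1, divided by 7".

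**The concern.** The example given with the summing rule is two steroids taken on one day, and adding those is right. A change of dose of one steroid would naturally be recorded as an earlier and a later record. If the earlier record has an incomplete stop date, 9.4.3 carries it past the change and 9.5.16 adds it to its successor. Nothing in 9.4.3, 9.5.16 or Appendix 4 separates succession from concurrent use.

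The endpoint measures dose reduction, so records of dose changes decide who responds. The cumulative prednisone dose (9.5.16.3) and the treatment-completion dose (9.5.16.1) use the same daily totals. The one planned sensitivity analysis (12.1.1) only drops the rule on new immunomodulatory agents and would not reveal the problem.

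**Working it through.** The plan states no responder rate, power or sample size for this endpoint, so there is no stated figure to reproduce. The dose pairs below are illustrative assumptions. With visits on schedule, Week 40 to Week 52 gives 83 dose-days and a divisor of 84.

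**1. Stop date missing, change before Week 40.** The old record covers the whole window.

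- Formula: average = 83 × (old + new) / 84; true average = 83 × new / 84.
- 10 to 5 mg/day: 83 × 15 / 84 = 14.82, against a true 83 × 5 / 84 = 4.94.
- 20 to 5 mg/day: 83 × 25 / 84 = 24.70, against 4.94.
- 7.5 to 5 mg/day, as a later step of a taper: 83 × 12.5 / 84 = 12.35.
- 5 to 2.5 mg/day: 83 × 7.5 / 84 = 7.41, still within the 7.5 limit.

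An old dose above 7.5 mg/day therefore rules out response whatever the new dose. (Strictly the limit is 7.5 × 84 / 83 = 7.59, because of the divisor.)

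**2. Stop date month-only, new dose in force for the whole window.** With k overlap days inside the window:

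- Formula: average = (83 × new + k × old) / 84. It exceeds 7.5 when k > (7.5 × 84 − 83 × new) / old.
- 10 to 5: (630 − 415) / 10 = 21.5, so 22 days.
- 20 to 5: 215 / 20 = 10.75, so 11 days.
- 10 to 2.5: (630 − 207.5) / 10 = 42.25, so 43 days, which one calendar month cannot supply.

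Thirty overlap days add 30 × old / 84: 3.57 mg/day for an old dose of 10 and 7.14 for 20.

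**3. One-step tapers over a year of start dates.** I applied the 9.4.3, 9.5.16 and 12.1.1 rules with the 83/84 window and counted the true responders who become non-responders.

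| Change inside Weeks 40–52 | 7.5 to 5 | 10 to 5 | 10 to 2.5 | 5 to 2.5 |
|---|---|---|---|---|
| Stop date month-only | about 47% | about 62% | about 35% | 0% |
| Stop and next start both month-only | about 80% | about 80% | about 43% | 0% |
| Stop date missing | 98–99% | 100% | 100% | 0% |

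Over all change dates from about Day 28, the month-only losses for the first three pairs are about 7–19%. A separate grid with old doses of 10 to 40 mg/day gave 5–12%. In that grid none of 13,542 scenarios per dose pair changed when the taper ended more than a month before Week 40.

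**4. Year-only stop dates.** The old record runs to 31 December or to completion/withdrawal, so the overlap can last months and approach case 1.

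**5. Baseline.** A 10 mg/day record truly stopped before the 7-day window, but its stop date is month-only in the month of Day 1. The subject takes 5 mg/day.

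- Derived baseline: 10 + 5 = 15 instead of 5, so the subject wrongly enters the subset above 7.5 mg/day.
- Staying on 5 mg/day gives 4.94 in the window, a reduction of 1 − 4.94 / 15 = 67%: a false responder.

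**6. Treatment comparison.** Assume true rates of 20% and 15%, with 80–95% of true responders kept in both arms. The difference falls from 5 points to 4.0–4.75, and the odds ratio from 1.42 to 1.40–1.41. False responders would act on top of this.

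**The case against.** The best defence is that the problem may be rare. Protocol 5.5.2 has SLE medications, with steroid dose and frequency, recorded at each visit, and Protocol 10.5 describes automatic and manual queries for consistency and completeness. Two open records of one steroid could be caught there. Neither the eCRF layout nor the ADPRED specification is in the documents, so recording a dose change as two records is an inference. The RAP also describes the efficacy endpoints as secondary in nature. All of this stands and limits the weight of the point. It does not remove it: no document specifies such a query, and the RAP writes a stop-date rule specifically for corticosteroids, so it expects incomplete records.

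Three stronger readings are tempting, and the documents do not support them.

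- *That tapering subjects in general are scored as non-responders.* With month-only dates the overlap ends with the month, and most tapers completed well before Week 40 are untouched.
- *That the error only removes responders and so dilutes the treatment effect.* It only adds dose, but dose added at baseline can create responders. In the other direction, a partial start date in the month of treatment start is normally set to the treatment start date, which takes that record out of the baseline window.
- *That complete dates also fail when stop and start share a day.* One day adds old / 84, or 0.12 mg/day for an old dose of 10, and the 84 divisor for 83 dose-days partly or wholly offsets it. Only 0–5% of true responders change in the pairs tested with the change inside Weeks 40–52. This is negligible and no part of the point.

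**Conclusion.** The point holds. Applied as written, the rules give a wrong daily dose whenever a superseded record of the same steroid has an incomplete stop date that carries it past the change. The consequence is decisive for a missing stop date on an old dose above 7.5 mg/day changed before Week 40. It is conditional for month-only dates: about 35–80% of true responders lost if the change falls in Weeks 40–52, about 7–19% over all change dates, and none for pairs as low as 5 to 2.5 mg/day. Both ranges rest on assumed dose pairs, a single change per subject and on-schedule visits.

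The bias can run either way. Its net effect on the treatment comparison cannot be computed, because the documents do not say how many steroid records have incomplete dates. The rule should be corrected; the documents do not show that the efficacy conclusion is wrong.

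**What to change.** Add to 9.5.16: when consecutive records of the same SLE steroid and route overlap solely because a partial or missing date was imputed, end the earlier record on the day before the later one starts. If both dates are partial in the same month, use one common mid-month change date. The adjustment should move the imputed date and never overwrite a recorded one.

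Do not apply this to records flagged as ongoing, or to split-dose or otherwise concurrent regimens. Appendix 4 lists QAM, QPM and QHS frequencies, so a morning and an evening record of one drug may both be valid. Keep summing different steroids and concurrent records with complete dates. Report the number of imputed steroid dates by arm.

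The Years 2 to 5 RAP records that the Week 52 data were unblinded on 2-JAN-2019. For those results the corrected derivation should be a labelled sensitivity analysis beside the planned one.

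The cost is a sentence or two in the RAP, a few lines in the ADPRED program and one extra table. The downside is slight under-counting of a genuine top-up of the same steroid whose stop date is incomplete. A superseded record wrongly left as ongoing would still be double-counted and needs a data query.
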